4.2.3.6 Dose Calculation

Doses are to be calculated with CT based heterogeneity corrections, i.e. corrections are made for density differences between air spaces, lungs, water-density, or bone tissue.

5. Symptom Assessment during Protocol Treatment

A) As noted below in “Evaluation of Outcomes of Interest,” patients will be evaluated in the clinic for toxicity at follow-up visits every 8 +/- 2 weeks until 1 year, and then less frequently thereafter. Concordant with these clinic visits, the research team will capture toxicities in our toxicity log that meet the following criteria, per institutional policy: a) severe, defined as CTCAE v4.0 Grade 3 or higher, 2) unexpected, or 3) unanticipated. In addition, we will ensure that all relevant toxicities (severe, unexpected, or unanticipated) are documented appropriately in the medical record.

B) *Multiple-symptom assessment tool (optional)*. Symptoms will be measured by the Lung Cancer module of the MDASI²⁴. The MDASI is a multiple-symptom measure of cancer-related symptoms²⁵ that is sensitive to disease and treatment changes in lung cancer. This instrument is brief, easily understood, and validated in the lung cancer population. Patients rate the intensity of physical, affective, and cognitive symptoms on 0–10 numeric scales, ranging from “not present” to “as bad as you can imagine.” Patients also rate the amount of interference with daily activities caused by symptoms on 0–10 numeric scales, ranging from “did not interfere” to “interfered completely.” The MDASI-LC has 3 additional items known to be important in assessing patients with MM or MM therapies (constipation, coughing, sore throat). The MDASI-LC takes less than 5 minutes to complete. It can be completed at home using the web or an interactive voice response-computer system that calls the patient to have them rate their symptoms and symptom interference²⁶. Symptom severity and interference over time will be a secondary endpoint. The MDASI is included in Appendix C, and this data will be collected from each patient at each follow-up visit as described in the *Evaluation of Outcomes of Interest* section (every 6-8 weeks for the first year).

6. Optional Procedures after Induction Chemotherapy

A) Tissue specimen collection for biomarker analysis:

[figure not shown]

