7.4 Design

Design Assumptions:

Primary endpoint	Progression-free survival (PFS)
Null hypothesis	Median PFS equals to 4 months in both groups
Alternative hypothesis	Median PFS equals to 4 months in the delayed/no LCT group and equals to 7 months in the immediate LCT group.
Associated hazard ratio	0.57 = 75% improvement in median PFS
Type I error	10%
Type II error	10%
Accrual rate	2-3 patients/month
Follow-up	9 months

A design with one-sided 10% type I error and 90% power would require an expected number of progression events of 87 under the alternative hypothesis to detect 75% improvement in median PFS. Given these assumptions, this design would require 94 patients *randomized* over 37.6 months with additional 9 months of follow-up. One interim analysis will be performed to allow for the early termination of the trial in light of evidence that the LCT arm is superior to the no LCT arm or there is no difference between the two treatment arms. In order to provide an overall significance level of 0.05 for the study, the interim analysis will use a Lan-DeMets monitoring boundary with an O'Brien-Fleming stopping rule (East 5.4.2.0, Cytel 2011). The interim analysis will be performed when 44 out of the expected 87 events have been observed. Using O'Brien-Fleming test boundaries, the Z-score test cut-off at the interim analysis for stopping and rejecting the null hypothesis will be 2.054, the Z-score test cut-off at the interim analysis for stopping and rejecting the alternative (futility) is -0.203.

In order to obtain 94 patients for randomization, we estimate that 25% of patients (24) will undergo progression of disease during induction chemotherapy based on the first 6 months of patient enrollment. In addition, we anticipate that 20% of patients (19) will refuse randomization after up-front systemic therapy. Therefore, in order to randomize 94 patients, we anticipate that we will need to enroll $94 + 24 + 19 = 137$ patients. Note that patients who cross-over to the alternative treatment arm due to toxicity will be censored at the time of crossover, with the last progression-free date being the date of crossover.

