7.5 Statistical Analysis Plan

Descriptive statistics will be provided to summarize the patient characteristics and toxicities by the treatment arms (immediate LCT and delayed/no LCT groups). Chi-square test or Fisher's exact test will be applied to compare patient characteristics between the two arms. The balance of the five prognostic covariates (used in the Pocock-Simon's dynamic allocation method) between the two arms will be examined as well. For the primary endpoint, PFS, Kaplan-Meier estimate will be computed, and the log-rank test will be performed to compare the difference of PFS between the two arms. Cox regression model will be applied to correlate PFS with potential covariates in both the univariate and multi-covariate analyses. Patients are considered evaluable for efficacy if they receive at least one of the intended local consolidation therapy. Both the intent-to-treat analysis and analysis among the evaluable patients will be performed. The corresponding results will be compared and contrasted. For the secondary endpoints, similar analysis will be performed on the overall survival and other time-to-event endpoints. Safety and tolerability of the immediate LCT arm and delayed/no LCT arm will be summarized by descriptive statistics. Quality of life will be analyzed by the repeated measures analysis of variance to count for the change before and after treatment and during the follow-up period. Proper transformation will be performed if necessary to transform data to be closer to the Gaussian distribution. All the statistical analyses will be two-sided with a P-value of 0.10 or less considering statistically significant.

Note that the MDACC DSMB will be providing study-wide oversight in regards to the endpoints described above.

To account for patients that crossover for reasons other than RECIST progression of disease (e.g. toxicity, growth of the malignancy that does not constitute RECIST progression), censoring will occur at the time of crossover for our primary analysis. In addition, a secondary time varying covariate Cox model analysis will be done to assess the impact of crossover without RECIST progression.

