7.6 Off-study criteria

Patients who enroll on Step 1 will be followed for survival status prior to step 2 if they: 1) progress on chemotherapy, 2) experience toxicity that is deemed to be unacceptable by the treating physician prior to the minimum requirements for induction chemotherapy (i.e. 4 cycles of platinum doublet therapy, 3 months of erlotinib/ afatinib, or 3 months of crizotinib), or 3) refuse randomization. If this occurs, they will remain on study only until proceeding to LCT at the end of induction chemotherapy, if applicable (e.g. without any maintenance therapy or second line systemic therapy), and will be followed for survival status at the conclusion of LCT. Allowing patients to remain on study until the time of LCT will allow for tissue collection if the patient proceeds to surgical resection. Patients who do not proceed with randomization but do not proceed immediately to LCT (receiving maintenance therapy or further systemic therapy) will be followed for survival status immediately after proceeding to maintenance therapy or further systemic therapy.

Patients who continue to step 2, or enroll at step 2, will be followed for survival status at the time of RECIST progression. Patients that are randomized to the immediate LCT arm will be followed for survival status immediately after experiencing RECIST progression. Patients that are randomized to the delayed LCT arm that experience progression will remain on study until the completion of LCT *only if LCT is planned within 6 weeks*. In this scenario, the patient will be followed for survival status at the conclusion of LCT. If no LCT is planned within this timeframe (i.e. if second line chemotherapy is planned and not LCT), the patient will be followed for survival status immediately after experiencing RECIST progression. Allowing patients to remain on study until the time of LCT will allow for tissue collection at that time if the patient proceeds to surgical resection. At that time, crossover can occur between treatment arms, at the treating physician's discretion. Crossover can also occur due to treatment toxicity or an increase in the size of disease that does not meet the criteria of RECIST progression. Patients who do not meet the criteria for RECIST progression and crossover to the alternate arm (e.g., crossover for a reason other than progression) will remain on study and will be followed for survival status.

8. Evaluation of Outcomes of Interest

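### Toxicity is summarized by arm with no account of time observed, although observation appears to end at progression and the delayed arm's window can extend through its LCT

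*Combined protocol and SAP*

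**What the plan says.** Safety and tolerability of LCT is a secondary objective (section 1.2). Its analysis in section 7.5 is one sentence: "Safety and tolerability of the immediate LCT arm and delayed/no LCT arm will be summarized by descriptive statistics". The opening of 7.5 likewise promises a descriptive summary of toxicities by arm. Neither place gives a window, a person-time denominator or a time-to-event method.

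Four places bear on how long toxicity is observed:

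- Section 4.0 follows every patient to documented progression, with a cap two years after randomization.
- Section 7.6 says "Patients who continue to step 2, or enroll at step 2, will be followed for survival status at the time of RECIST progression". It makes an exception for one arm: "Patients that are randomized to the delayed LCT arm that experience progression will remain on study until the completion of LCT", provided that LCT is planned within 6 weeks. The reason given is tissue collection.
- Section 5, item A, says "patients will be evaluated in the clinic for toxicity at follow-up visits every 8 +/- 2 weeks until 1 year" and less often after that. Toxicities are logged in step with those visits. Progression is not mentioned.
- Appendix A lists a toxicity assessment at each 8-week visit to week 48, again with no stop at progression.

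**The concern.** If toxicity is recorded only while a patient is on study, and on-study time ends at progression, then time at risk for a logged toxicity is close to PFS itself, the outcome that LCT is meant to lengthen. A percentage of patients with toxicity then mixes risk with length of observation. The delayed-arm exception adds a second difference: some control patients are watched through an LCT course after progression, while immediate-arm patients are not watched after progression at all.

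The risk-benefit reading of LCT is at stake. The primary PFS comparison is not affected.

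**Working it through.** **Inputs.** Section 7.4 gives the medians, "Median PFS equals to 4 months in the delayed/no LCT group and equals to 7 months in the immediate LCT group", and the hazard ratio, "0.57 = 75% improvement in median PFS" (4/7 = 0.571). It also says "A design with one-sided 10% type I error and 90% power would require an expected number of progression events of 87 under the alternative hypothesis" and "this design would require 94 patients *randomized* over 37.6 months with additional 9 months of follow-up". Section 4.0 gives 1:1 allocation and the 24-month cap. I assume exponential PFS, so the monthly hazards are ln 2/4 = 0.1733 (delayed/no LCT) and ln 2/7 = 0.0990 (immediate LCT). PFS stands in for the end of observation.

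**Reproducing the plan's figure.** With 47 patients per arm accrued uniformly over 37.6 months plus 9 months, the expected events are 47 times the average of 1 − exp(−λt) for t from 9 to 46.6 months. This gives 45.5 + 41.9 = 87.4, against 87 stated. The exponential inputs fit the design.

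**Mean observation to progression.** The formula is (1 − exp(−λT))/λ.

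| Window | Delayed/no LCT | Immediate LCT | Ratio |
|---|---|---|---|
| T = 24 months | (1 − 0.0156)/0.1733 = 5.68 | (1 − 0.0929)/0.0990 = 9.16 | 1.61 |
| 24 months and end-of-study censoring | 5.54 | 8.67 | 1.56 |
| 48-week Appendix A grid (11.08 months) | 4.92 | 6.73 | 1.37 |

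**Adding the delayed-arm extension.** The documents do not say how many delayed-arm progressors go promptly to LCT. I assume that a fraction f stays e months longer, with f from 25% to 100% and e from 1.38 months (6 weeks) to 2.38 months (6 weeks plus an assumed month for LCT). The delayed-arm mean becomes 5.68 + f × e × 0.984.

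- f = 25%, e = 1.38: 6.02 months, ratio 1.52.
- f = 100%, e = 2.38: 8.03 months, ratio 1.14.
- On the 48-week grid the same two cases give ratios of 1.29 and 0.97.

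**Patients with at least one toxicity at equal risk.** With the same constant hazard r in both arms, the 24-month cap and no extension, the share is r/(r + λ) × [1 − exp(−24(r + λ))]. The values of r are assumptions, because the documents give no toxicity rate.

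| r per month | Delayed/no LCT | Immediate LCT | Ratio |
|---|---|---|---|
| 1% | 5.4% | 8.5% | 1.58 |
| 5% | 22.3% | 32.6% | 1.46 |
| 20% | 53.6% | 66.8% | 1.25 |

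**Early toxicity.** If toxicity can arise only in the first 2 or 3 months, the ratio of mean time at risk is 1.07 or 1.11.

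**Checking candidate summaries at equal risk, without the extension.**

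- Events per patient-month: with the risk confined to the first 3 months, the rate ratio is 1.109/1.613 = 0.69. The LCT arm would look safer only because its later months carry no risk.
- Cumulative incidence with progression as a competing event, r = 5%, 24 weeks (5.54 months): r/(r + λ) × [1 − exp(−5.54(r + λ))] gives 15.9% against 18.9%. Part of the artefact remains.
- Cumulative incidence with censoring at the end of observation, same r and time: 1 − exp(−0.05 × 5.54) = 24.2% in both arms, provided that progression carries no information about toxicity.

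**The case against.** A reader might infer that section 7.6 stops toxicity collection at progression. It does not say so: it never mentions toxicity, and section 5A and Appendix A show visits with no such stop. The stop is an inference from 4.0 and 7.6 read together. It is a natural one, since 7.6 justifies keeping patients on study by tissue collection, which suggests that study collection otherwise ends. It is still not stated.

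A reader might also infer that the LCT arm is watched 1.6 times as long, must show more toxicity, and is therefore judged too harshly. The documents do not support that either. The 1.6 leaves out the delayed-arm extension. LCT at progression is named in that arm's own heading (4.2.1), so it may not be rare, and it puts LCT toxicity into the delayed arm's column. The 1.6 is also a ratio of time, not of patients affected, and matters less the earlier toxicity arises.

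It can fairly be added that descriptive statistics do not rule out rates or fixed windows, and that no test or decision rule rests on the toxicity table in this phase II trial of 94 randomized patients. These points limit the size and importance of the concern. They do not remove it: the plan commits to no window, and does not say when recording ends. Nor is all toxicity necessarily early. Both arms may receive maintenance therapy, and sections 2.3.1 and 2.3.2 report grade 3 or higher toxicity on it.

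**Conclusion.** The point holds as a gap in the safety analysis that is cheap to close. Section 7.5 ignores time observed, and the documents leave the end of toxicity recording to inference. If it ends at progression, the windows differ in length and content. The mean-time ratio is 1.61 under exponential PFS at the design medians with the two-year cap, about 1.5 to 1.1 after the extension under assumed uptake, as low as 0.97 on the 48-week grid, and near 1.1 for early toxicity before any extension.

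Crude percentages can differ at equal risk, for example 33% against 22% at an assumed constant 5% per month before the extension. The direction is not guaranteed once delayed LCT is included, so a claim of bias against LCT goes too far. If recording is instead meant to continue past progression, as 5A can be read, these ratios do not apply, but 7.6 and 5A still need to agree.

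**What to change.** First reconcile sections 4.0, 5A, 7.6 and Appendix A, and state when toxicity recording ends in each arm.

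Then amend 7.5:

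- Make the main between-arm summary the cumulative incidence of first grade 3 or higher toxicity from randomization, at fixed common times such as 8, 16 and 24 weeks. Censor at the end of toxicity observation, and state the assumption that this censoring is uninformative.
- List the delayed arm's toxicity after progression during LCT separately.
- Keep crude counts and events per patient-month as supplements. A rate should not lead, for the reason shown by the 0.69 above.

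The cost is a few sentences of SAP text and a few table columns. The toxicity log must also hold onset dates, or the visit dates that bound them; section 5A does not say that onset dates are recorded. The uninformative-censoring assumption cannot be checked fully, which is why it should be written down.

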1.2 Secondary Objectives

The secondary objectives of this study will be to:

- Determine the overall survival
- Safety/tolerability of LCT
- Time to progression of prior metastatic lesions
- Time to appearance of new metastases (CNS vs. extra-CNS, treated lesion vs. new site)
- Quality of life

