4.2 Immediate LCT (local consolidation therapy) Arm

Patients who undergo LCT will have ablation of all residual local and metastatic sites of disease by surgery and/or radiation therapy. The optimal form of LCT will be determined by the treating physician(s). Consultation with a multidisciplinary group including a medical oncologist, thoracic surgeon and radiation therapist is encouraged. After the completion of LCT the patient will be treated with surveillance or maintenance treatment as determined by medical oncologist and described below.

4.2.1 Delayed/No LCT Arm – LCT given at the time of progression or toxicity after maintenance therapy or observation

Prior to treatment with maintenance therapy, we recommend adequate hematologic function as defined by an absolute neutrophil count (ANC) $\geq 1,500/\text{mm}^3$, platelet count $\geq 100,000/\text{mm}^3$, WBC $\geq 3,000/\text{mm}^3$, and hemoglobin $\geq 9 \text{ g/dL}$ within 3 weeks of study entry. We also recommend adequate hepatic function as defined by a total bilirubin level $\leq 1.5 \times$ the upper limit of normal (Serum bilirubin $\geq 1.5 \times$ Upper Limit of Normal in the setting of known Gilbert's disease is allowed), and alkaline phosphatase, AST and ALT $\leq 2.5 \times$ the upper limit of normal or $\leq 5.0 \times \text{ULN}$ if liver metastases are present.

Currently, there is no single standard maintenance approach and treatment is typically chosen based on clinical factors and tumor features (e.g., histology and mutation status). Patients randomized to this arm will receive maintenance therapy (switch or continuation), or surveillance, based on physician choice. Pemetrexed, bevacizumab, crizotinib (for ALK-mutation positive patients) or erlotinib are recommended as acceptable maintenance agents but other agents may be used at physician discretion.

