C) Quality of life multiple-symptom assessment pool- see section 5B above.

7. Statistical Considerations

7.1 Preliminaries. The purpose of this study is to test the hypothesis that the treatment paradigm of immediate LCT after induced oligometastatic disease can lead to reduced rates of disease progression. Patients will be randomized between immediate LCT and delayed/no LCT arms. The primary outcome will be progression-free survival (PFS) time, defined as the time from the time of randomization (immediate LCT vs. delayed/no LCT) to disease progression or death. The primary goal will be to compare the PFS times of these two arms.

7.2 Database Used for Collection. Study data will be collected and managed using REDCap (Research Electronic Data Capture) electronic data capture tools hosted at MD Anderson. [ref] REDCap (www.project-redcap.org) is a secure, web-based application with controlled access designed to support data capture for research studies, providing: 1) an intuitive interface for validated data entry; 2) audit trails for tracking data manipulation and export procedures; 3) automated export procedures for seamless downloads to common statistical packages; and 4) procedures for importing data from external sources. In the case of multi-center studies REDCap uses Data Access Groups (DAGs) to ensure that personnel at each institution are blinded to the data from other institutions. REDCap (<https://redcap.mdanderson.org>) is hosted on a secure server by MD Anderson Cancer Center's Department of Research Information

Systems & Technology Services. REDCap has undergone a Governance Risk & Compliance Assessment (05/14/14) by MD Anderson's Information Security Office and found to be compliant with HIPAA, Texas Administrative Codes 202-203, University of Texas Policy 165, federal regulations outlined in 21CFR Part 11, and UTMDACC Institutional Policy #ADM0335. Those having access to the data file include the study PI and research team personnel. All protected health information (PHI) will be removed from the data when it is exported from REDCap for analysis. All dates for a given patient will be shifted by a randomly generated number between 0 and 364, thus preserving the distance between dates. Dates for each patient will be shifted by a different randomly generated number. Following publication study data will be archived in REDCap.

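### Toxicity is tabulated only by randomized arm, so LCT toxicity logged in delayed-arm patients sits in the comparator column and dilutes the between-arm contrast by an unstated fraction

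*Combined protocol and SAP*

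**What the plan says.** Section 1.2 names the safety objective as "Safety/tolerability of LCT", that is, the safety of the intervention rather than of an assigned strategy.

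Section 7.5 answers it by arm, in two places: "Descriptive statistics will be provided to summarize the patient characteristics and toxicities by the treatment arms (immediate LCT and delayed/no LCT groups") and "Safety and tolerability of the immediate LCT arm and delayed/no LCT arm will be summarized by descriptive statistics". These are the randomized arms. Section 7.1 states: "Patients will be randomized between immediate LCT and delayed/no LCT arms".

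LCT is also part of the comparator. The heading of Section 4.2.1 describes the delayed/no LCT arm as "LCT given at the time of progression or toxicity after maintenance therapy or observation". Section 7.6 gives two on-study routes:

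- At progression: "Patients that are randomized to the delayed LCT arm that experience progression will remain on study until the completion of LCT", on condition that LCT is planned within 6 weeks. What follows is "In this scenario, the patient will be followed for survival status at the conclusion of LCT".
- Without progression: "Crossover can also occur due to treatment toxicity or an increase in the size of disease" falling short of RECIST progression. These patients stay on study and are followed for survival status.

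Section 5 has toxicities that are grade 3 or higher, unexpected or unanticipated logged at clinic visits every 8 ± 2 weeks up to one year, and less often after that.

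**The concern.** The objective asks about LCT, while the table compares assignments, and the comparator contains LCT by design. A severe toxicity caused by LCT in a delayed-arm patient, if logged, raises the delayed/no LCT rate and narrows the contrast that a reader would use to judge what LCT adds.

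The plan recognises the same problem for efficacy. Section 7.5 censors PFS at crossover without RECIST progression, adds a time-varying Cox model for such crossover, and defines an efficacy-evaluable set by receipt of LCT. Toxicity is the outcome most directly tied to receiving LCT, yet it has no counterpart: no safety set by LCT received, no timing from LCT start, and no split of delayed-arm toxicity at LCT start. At stake are a diluted safety contrast and unused LCT safety data from the delayed arm, in a trial with about 47 patients per arm.

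**Working it through.** **1. Inputs from the documents.** 94 patients randomized 1:1, so 47 per arm (Sections 4.0 and 7.4). Median PFS 4 months (delayed) and 7 months (immediate), 37.6 months of accrual, 9 months of further follow-up, and 87 expected events (Section 7.4). Follow-up to progression or two years (Section 4.0). The documents give no toxicity rate and no uptake of delayed LCT.

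**2. The plan's own figure.** With exponential PFS and uniform accrual, the probability of an event by the final analysis is

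1 − [exp(−9k) − exp(−46.6k)] / (37.6k), with k = ln 2 / median.

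- Delayed: k = 0.1733, probability 0.968, 47 × 0.968 = 45.5 events
- Immediate: k = 0.0990, probability 0.892, 47 × 0.892 = 41.9 events
- Total 87.4, which agrees with the stated 87

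So about 45.5 of 47 delayed-arm patients (97%) are expected to progress or die by the final analysis. This is a ceiling on those who could reach LCT at progression; how many would receive it is not stated.

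**3. Dilution.** Let pL be the toxicity risk with LCT, p0 the risk without it, and f the share of the delayed arm whose LCT toxicity risk is captured on study (uptake times completeness of capture). The delayed-arm rate is p0 + f(pL − p0), so

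by-arm difference = (1 − f)(pL − p0).

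All three quantities are assumptions:

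| pL vs p0 | True difference | f = 10% | f = 25% | f = 50% | f = 75% |
|---|---|---|---|---|---|
| 10% vs 3% | 7 points | 6.3 | 5.3 | 3.5 | 1.8 |
| 20% vs 5% | 15 points | 13.5 | 11.3 | 7.5 | 3.8 |
| 30% vs 10% | 20 points | 18 | 15 | 10 | 5 |

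**4. Pull in the other direction.** Immediate-arm patients are on study until RECIST progression, which the design assumes comes later. Mean time to a PFS event, capped at 24 months, is (1 − exp(−24k))/k: 5.7 months delayed and 9.2 months immediate. Add an assumed background rate h of severe events per month, equal in both arms. The crude proportion with an event is

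h/(h + k) × [1 − exp(−24(h + k))].

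- h = 0.005: 2.8% delayed, 4.4% immediate, difference 1.6 points
- h = 0.03: 14.6% delayed, 22.2% immediate, difference 7.6 points

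This gap counts against the immediate arm with no true effect of LCT. It ignores the extra on-study time of delayed-arm patients kept through LCT, which would reduce it.

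**5. Comparing the two.** At 20% vs 5%, dilution removes 15f points: 1.5 at f = 10% and 7.5 at f = 50%. That range overlaps the 1.6 to 7.6 points from unequal observation. The models are rough, but they are enough to show that the documents do not fix the net sign.

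**6. Data left unused.** If all 47 immediate-arm patients receive LCT, the number of LCT recipients with captured toxicity is 47(1 + f): about 52 at f = 10%, 59 at f = 25% and 71 at f = 50%.

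**The case against.** The strongest reply is that the by-arm table is the right randomized comparison. Delayed LCT belongs to the comparator strategy, safety is only descriptive, and no formal test of toxicity is planned. The immediate-arm column, where LCT is the assigned treatment, already describes LCT toxicity and does not change with f. All of this stands, so the gap is a missing supplementary analysis and the by-arm table should remain.

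A reader might infer that LCT's harm is understated, or that LCT will look safer than it is. The documents do not support that, because longer observation of the immediate arm pushes crude proportions the other way.

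A reader might also infer that all LCT toxicity in delayed-arm patients lands in the comparator column. That is not established. Patients treated at progression pass to survival follow-up when LCT ends, so later toxicity is lost rather than misplaced. The reason Section 7.6 gives for keeping them on study is tissue collection. Section 4.0 ends follow-up at documented progression or two years. For crossover without progression, Section 7.6 mentions survival follow-up but not toxicity. Capture is therefore partial at best, and f lies below uptake.

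The tempting remedy of pooling all LCT recipients and resting the objective on that set can itself mislead. As an assumed example, take 20% LCT toxicity in 47 immediate recipients and half of it captured (10%) in 28 delayed recipients. The pooled rate is (47 × 20% + 28 × 10%)/75 = 16.3%, below the 20% in the immediate arm.

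**Conclusion.** The point holds as a mismatch between objective and analysis. Section 7.5 offers only by-arm toxicity summaries for an objective about LCT, and LCT toxicity logged in delayed-arm patients is tabulated under delayed/no LCT. The by-arm contrast shrinks by the factor (1 − f): slightly if few delayed-arm patients have captured on-study LCT, by half if f = 50%. This rests on LCT toxicity being the same in both arms when captured and on assumed values for f, pL and p0.

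Two limits apply. The immediate arm's absolute toxicity rate is not affected. The net direction of bias in the crude contrast cannot be determined from the documents. The by-arm table alone therefore cannot show what LCT adds. The primary endpoint and sample size are not touched.

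**What to change.** Keep the by-arm table, with the immediate-arm summary as the main description of LCT safety. Add to Section 7.5:

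1. Delayed-arm toxicity split into before and after the start of any LCT. Use the part before LCT as the no-LCT comparator, and report it with on-study time or as exposure-adjusted rates alongside the immediate arm.
2. A supplementary descriptive table of toxicity from LCT start in all LCT recipients, with immediate and delayed recipients shown separately, over the same post-LCT window where observed, and with the number still under toxicity observation.

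Reconcile Sections 4.0, 5 and 7.6 so that it is clear whether toxicity is collected in delayed-arm patients during LCT given at progression and after crossover without progression.

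The cost is two descriptive tables, with no change to sample size or treatment. The comparison by exposure is not randomized and must be labelled descriptive. Delayed recipients are treated later in their disease, many after progression, and their post-LCT capture is partial. The documents do not state that LCT start dates and toxicity onset dates are recorded, so this must be confirmed first. Dates of crossover without progression are needed anyway for PFS censoring.
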